2. LIST OF ABBREVIATIONS

Abbreviation	Definition
AE	Adverse Event
AEM	Adverse Event Monitoring
AL	Light Chain Amyloid
ATTR	Transthyretin Amyloid
ATTR-CM	Transthyretin Amyloid Cardiomyopathy
ATTRwt-CM	Wild-type Transthyretin Amyloid Cardiomyopathy
CPT	Clinical Procedural Terminology, Fourth Edition
DrPH	Doctor of Public Health
EHR	Electronic Healthcare Records
FASA	Fellow of American Statistical Association
FDA	Food and Drug Administration
FN	False Negative
FP	False Positive
GPP	Guidelines for Good Pharmacoepidemiology Practices
GRACE	Good ReseArch for Comparative Effectiveness
hATTR-CM	Hereditary or Familiar Transthyretin Amyloid Cardiomyopathy
HCPCS	Healthcare Common Procedure Coding System
HF	Heart Failure

Abbreviation	Definition
HIPPA	Health Insurance Portability and Accountability Act
ICD-10	International Classification of Diseases, Tenth Revision
ICD-10-CM	International Classification of Diseases, Tenth Revision, Clinical Modification
ICD-10-PCS	International Classification of Diseases, Tenth Revision, Procedural Classification System
ICMJE	International Committee of Medical Journal Editors
IDN	Integrated Delivery Network
IEC	Independent Ethics Committee
IRB	Institutional Review Board
ISPE	International Society for Pharmacoepidemiology
ISPOR	International Society for Pharmacoeconomics and Outcomes Research
MA	Master of Arts
MBA	Master of Business Administration
MD	Doctor of Medicine
ML	Machine Learning
MPH	Master of Public Health
MS	Master of Science
NDC	National Drug Code
NIM	Non-inferiority Margin

Abbreviation	Definition
NIS	Non-interventional Study
NLP	Natural Language Processing
PharmD	Doctor of Pharmacy
PhD	Doctor of Philosophy
QC	Quality Control
RA	Rheumatoid Arthritis
RWE	Real World Evidence
TN	True Negative
TP	True Positive
TTR	Transthyretin
wtATTR-CM	Wild-Type Transthyretin Amyloid Cardiomyopathy
US	United States

4. ABSTRACT

Title: A retrospective validation study evaluating the performance of machine learning (ML) algorithm to identify chart-based clinical diagnosis of wild-type transthyretin amyloid cardiomyopathy (ATTRwt-CM) and non-amyloid heart failure among patients with heart failure (HF)

Version 1.0, 27 July 2023

PPD MPH, Pfizer, Inc.

Rationale and background: To identify suspected patients with ATTRwt-CM, Pfizer developed and assessed a ML model using a large, nationally representative database with subsequent performance evaluations in multiple different claim- and EHR-based databases.^{1,12-15} This model used patient's medical claims data to differentiate potential ATTRwt-CM patients from those who suffered from other causes of HF among HF patients 50 years of age or older. **CCI**

[REDACTED] The care provider can determine if the identified patient requires further evaluation and/or referral to other appropriate healthcare providers is needed. This tool may facilitate early and accurate diagnosis of ATTRwt-CM.

CCI

[REDACTED]

[REDACTED]

[REDACTED]

The ML model was developed using an operating definition of suspicious ATTRwt-CM patients with the presence of E85.82, an ICD-10-CM (International Classification of Diseases, Tenth Revision, Clinical Modification) diagnosis code. However, the ICD-10-CM code is an administrative code used for billing purpose. Therefore, an additional clinical study will be required to validate that the ML algorithm can accurately identify patients with clinically confirmed ATTRwt-CM among HF patients 50 years of age or older.

Study objective: This study aims to evaluate the performance of the ATTRwt-CM ML model to predict the clinical diagnosis of ATTRwt-CM among HF patients against chart-review-based ground truth with a prespecified performance thresholds in sensitivity and specificity.

Study design: This is an observational, retrospective non-inferiority study with a study sample from a large national EHR database integrated with administrative claims.

PFIZER CONFIDENTIAL

Population: This study will include HF patients ≥ 50 years old with clinical diagnosis of ATTRwt-CM or non-amyloid HF ascertained by charts. Patients will be required to have ≥ 12 months of continuous activity in the EHR or claims prior to the Index Date. There will be no minimal follow-up period for patients in this study.

Data source: Optum's Electronic Health Record and Integrated Claims-Clinical database that combines adjudicated claims data (where available) with Optum's EHR data, are the data sources for this study. In addition, this study will use data available in the unstructured for a subset of ATTRwt-CM and non-amyloid heart failure among patients with HF that have clinical patient notes and other data that cannot be mapped into the larger structured database. Optum's longitudinal repository is derived from dozens of healthcare provider organizations in the US, that include more than 57 contributing sources and 111K sites of care: treating more than 106 million patients receiving care in the US.

Sample size: Using various keyword search, feasibility assessment was performed. In the Optum EHR data, there were 422 potential ATTRwt-CM records available; yet, before reviewing the unstructured notes, one is unable to determine the total number of clinically diagnosed ATTRwt-CM patients. Given that ATTRwt-CM is a rare disease, the team will attempt to maximize the number of potential cases by performing note review for all 422 charts. Similar number of control charts will be reviewed to balance the number of cases and controls. We estimate that the sample sizes will likely provide 90% power to satisfy the non-inferiority hypotheses.

Data analysis: The ML model will identify patients with HF as suspected ATTRwt-CM and the remainder patients as not suspected for ATTRwt-CM/non-amyloid heart failure. The patients with HF will be entered in the ML algorithm along with their diagnosis codes listed in all their records. The model will classify patients based on the presence and absence of cardiac and non-cardiac features and categorized as suspected (at-risk) or not suspected with ATTRwt-CM. The model performance metrics (sensitivity and specificity) will be calculated based on the concordance between case ascertainment of ATTRwt-CM using diagnostic codes with ascertainment using clinical patient notes review, the latter using a variety of criteria to define ATTRwt-CM.

5. AMENDMENTS AND UPDATES

None.

6. MILESTONES

Milestone	Planned date
Start of data collection	September 1, 2023
End of data collection	October 31, 2023
Final study report	November 30, 2023

7. RATIONALE AND BACKGROUND

Transthyretin amyloid cardiomyopathy (ATTR-CM) is a rare condition that is an unrecognized cause of heart failure. The typical clinical presentation includes signs and symptoms of heart failure. The existing natural history data of the disease is poor, with ATTRv-CM and ATTRwt-CM having an estimated median survival of 2.5 years and 3.6 years after diagnosis respectively, and typically resulting from progressive heart failure or sudden death.²⁻⁴ Because the symptoms are heterogeneous, including both cardiac and non-cardiac involvement, the diagnosis of ATTR-CM, including ATTRwt-CM, is often delayed, or missed.^{2,5} Early diagnosis of ATTR-CM is key as progression worsens rapidly; however, diagnostic delay and misdiagnosis of ATTR-CM is common, with a reported mean time to diagnosis of 6.1 years in ATTRwt-CM.⁶ Current diagnostic tools include speckle-tracking echocardiography, cardiac magnetic resonance imaging with contrast, bone scintigraphy, and/or blood tests for amyloidogenic light chain amyloid. Recent expert consensus recommendations and clinical “red flag” clues have been established to help raise suspicion of ATTR-CM and have been classified into cardiac features (i.e., heart failure, atrial fibrillation) and extracardiac features (i.e., history of carpal tunnel syndrome).⁷⁻¹¹ A screening tool that raises greater clinical awareness of these “red flags” may help raise suspicion and identification of the ATTRwt-CM.

In an effort to identify suspected patients with ATTRwt-CM, Pfizer developed and validated a random forest-based ML risk prediction model using a large, nationally representative database with subsequent validation and performance in multiple additional cohorts.^{1,12-15} This model identified patient characteristics that could be used to differentiate ATTRwt-CM from other causes of HF among HF patients 50 years of age or older. This model showed an association between clinical features that were associated with ATTRwt-CM using US medical claims. CCI [REDACTED]
[REDACTED]
[REDACTED]

In developing the ML algorithm, the only clinical validation cohort confirmed the diagnosis of suspicious ATTRwt-CM patients identified by an algorithm using the presence of an ICD-10 (International Classification of Diseases, Tenth Revision) diagnosis code, E85.82. ICD-10 code is an administrative code used for billing purpose and it likely may not be readily used as a gold standard to confirm a clinical diagnosis. The presence of a diagnosis code may mean that the patient has a clinical diagnosis; however, it also often means that the clinician may screen the patient for the disease, which requires further clinical information to confirm the diagnosis. Given this, an additional clinical validation study is vital to ensure that the ML algorithm can predict the risk of clinically confirmed ATTRwt-CM among patients with HF.

8. RESEARCH QUESTION AND OBJECTIVES

[figure not shown]
This study aims to further evaluate the performance of the ATTRwt-CM ML model to predict the clinical diagnosis of ATTRwt-CM among HF patients against chart-review-based ground truth with a prespecified performance thresholds in sensitivity and specificity.

9. RESEARCH METHODS

9.1. Study Design

[figure not shown]
This is a retrospective cohort study. Patients with HF who meet inclusion and exclusion criteria will be identified from the Optum EHR database between 01 January 2018 and 30 April 2023. A subset of patients with clinical diagnosis of ATTRwt-CM or non-amyloid heart failure ascertained by charts will be included in this study (study population). Detailed methodology of clinical diagnosis ascertainment is found in [Appendix A](#). Patients will be indexed at their latest heart failure diagnosis or treatment date and will be required to have ≥ 12 months of activity before the index date. There will be no minimal follow-up period for patients in this study.

Figure 1. Study Design

The ML algorithm will calculate the predicted probability of ATTRwt-CM for these heart failure patients based on the presence and absence of features (demographics, clinical diagnosis, etc.) during the pre-index period. Detailed ML algorithm methodology can be found in Huda et al.¹ Based on a pre-specified predicted probability threshold of 0.5, we will further classify these patients as suspected ATTRwt-CM (predicted probability ≥ 0.5) and not suspected with ATTRwt-CM/non-amyloid heart failure (predicted probability < 0.5). The model performance metrics (sensitivity and specificity) will be calculated by cross-tabulating diagnosis based on ML algorithm and diagnosis based on chart ascertainment.

Figure 2. Evaluating ML Model Performance

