9.3. Derived Variables

Variable	Role	Operational definition
HF	Index	
• Latest claim/encounter for HF or HF treatment (see Appendix B for the code list)
ATTRwt-CM	Exposure	
• Confirmed: Ground truth ascertained by charts• Suspected ATTRwt-CM: Identified by the ML algorithm (predicted probability ≥ 0.5)• Not Suspected with ATTRwt-CM/non-amyloid heart failure: Identified by the ML algorithm (predicted probability < 0.5)

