9.7. Data Analysis

9.7.1. Statistical Methods

The ML model will identify patients with HF as suspected ATTRwt-CM and the remainder patients as not suspected for ATTRwt-CM/non-amyloid HF. The patients with HF will be entered in the ML algorithm along with their diagnosis codes listed in all their records. The model will classify patients based on the presence and absence of cardiomyopathy features and categorized as suspected (at-risk) or not suspected with ATTRwt-CM. The model performance metrics (sensitivity and specificity) will be calculated by cross-tabulating between diagnosis based on ML algorithm and diagnosis based on chart ascertainment.

The analyses for noninferiority of sensitivity and specificity are straightforward. The calculations for these measures are shown below.

PFIZER CONFIDENTIAL

CT24-WI-GL02-RF02 4.0 Non-Interventional Study Protocol Template For Secondary Data Collection Study

01-Jun-2022

Page 19 of 25

Table 1. Sensitivity and Specificity

ML classification	Cohort (Ascertained by Charts)		TP+FP
	ATTRwt-CM	Non-amyloid HF	
+	True Positive (TP)	False Positive (FP)	TP+FP
-	False Negative (FN)	True Negative (TN)	TN+FN
	TP+FN	TN+FP	

Sensitivity = TP / (TP + FN)

Specificity = TN / (TN + FP)

We would then calculate the one-sided 95% confidence interval (CI) for sensitivity, assuming 90% power:

$$95\% \text{ CI} = \text{sensitivity} - 1.645(\text{SE}_{\text{sensitivity}})$$

where $\text{SE}_{\text{sensitivity}} = \text{square root} [\text{sensitivity} - (1-\text{sensitivity})]/n_{\text{sensitivity}}$

The 95% CI for sensitivity must equal or exceed a cut point (CP) value between 0.80 and 0.90 where:

$$\text{CP} = 0.90 - \text{NIM Z1-} \beta / (\text{Z1-}\alpha + \text{Z1-}\beta)$$

When $\alpha = 0.05$ and power = 0.90 we reject inferiority for all values $\geq \text{CP} = 0.8561$.

Similarly, for specificity, we reject inferiority for all values $\geq \text{CP} = 0.7761$.

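### Indexing every patient at the latest heart failure date lets cases be scored on coding made during or after the amyloid work-up, so primary sensitivity may describe patients already recognised

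*Combined protocol and SAP*

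**What the plan says.** Section 9.1 fixes the index date: "Patients will be indexed at their latest heart failure diagnosis or treatment date". Section 9.3 gives the same definition. Patients are "identified from the Optum EHR database between 01 January 2018 and 30 April 2023", and at least 12 months of activity before index is required (Sections 9.1 and 9.2.1). The model then scores each patient "based on the presence and absence of features (demographics, clinical diagnosis, etc.) during the pre-index period".

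Cases are patients with ATTRwt-CM ascertained from charts (Sections 9.2.1 and 9.6). The controls, patients with non-amyloid heart failure, are indexed by the same rule.

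The abstract and Section 9.7.1 describe the model's data differently. Section 9.7.1 says: "The patients with HF will be entered in the ML algorithm along with their diagnosis codes listed in all their records". The inputs are summarised as "based on the presence and absence of cardiac and non-cardiac features" in the abstract and "based on the presence and absence of cardiomyopathy features" in Section 9.7.1. Section 9.1 refers to a cited paper for the model's methodology.

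Section 9.2.1 lists indexing at the earliest heart failure date as a sensitivity analysis, subject to feasibility. Section 9.9 does not discuss when features were recorded relative to the amyloid diagnosis.

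**The concern.** A case enters the study because amyloid disease has already been recognised and written into the notes. If heart failure care continues afterwards, the latest heart failure date falls after recognition, and the pre-index features can include whatever was coded during or after the work-up. Related conditions may also be coded more fully once amyloid is suspected. Section 7 itself names carpal tunnel syndrome as a clue of this kind.

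The abstract presents the tool as a possible aid to earlier diagnosis. Patients in that setting have no such coding yet. If some cases are scored with it, primary sensitivity describes recognised patients and may be higher than the tool would achieve in unrecognised ones. As planned, a reader could not tell. The report need not give the share of cases indexed after recognition, and no analysis limited to earlier features is certain to be run.

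**Working it through.** **1. The plan's own figure.** Section 9.5 uses √N = (z₁₋α + z₁₋β)·√(p(1−p))/M. With one-sided α = 0.05, power 0.90, p = 0.90 and M = 0.10:

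N = (1.6449 + 1.2816)² × 0.09 / 0.01 = 77.07, rounded up to 78, as stated.

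The cut point is 0.90 − 0.10 × 1.2816/2.9264 = 0.8562, against 0.8561 stated. The concern does not rest on an arithmetic error.

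**2. Where the feature window ends.**
- Section 9.1: at the latest heart failure date.
- Abstract and Section 9.7.1, read literally: no end date.
- The two differ only from the latest heart failure date onward. Under either, the window can run past the work-up.
- The readable text contains no rule that ends the window at first suspicion, testing or diagnosis, or that removes codes arising from the work-up.

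**3. How often this could arise (illustration, not a bound).** The study window is W = 5.325 years (1 January 2018 to 30 April 2023), and median survival after ATTRwt-CM diagnosis is m = 3.6 years (Section 7). Assume exponential survival, diagnoses spread evenly over W, and heart failure care recorded until death, loss from the network or the end of the window. The share of cases whose latest heart failure date could fall at least t years after diagnosis is

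((W − t)/W) × exp(−(ln 2/m + k)·t), where k = −ln(1 − annual network loss).

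For t = 0.25, W = 5.325, m = 3.6, k = 0: 0.953 × 0.953 = 0.908.

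| Assumptions | t = 3 months | t = 12 months |
|---|---|---|
| W = 5.325, m = 3.6, no loss | 0.908 | 0.670 |
| W = 2, m = 3.6, no loss | 0.834 | 0.412 |
| W = 2, m = 1.8, 30% annual loss | 0.727 | 0.238 |
| W = 1, m = 1.8, 30% annual loss | 0.623 | 0 |

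Only the first row uses the documents' figures alone; the shorter windows, halved survival and network loss are assumed. Continuous recording matters as much. If only half of surviving, in-network patients had later heart failure records (assumed), the 3-month figures would run from 0.31 to 0.45.

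**4. What a lift would do (assumed values).** Let s₀ be sensitivity on features recorded before the work-up, and g the share of otherwise missed cases turned positive by later coding. Observed sensitivity is s₀ + g(1 − s₀). With s₀ = 0.80, the null value, g = 0.25 gives 0.85 and g = 0.50 gives 0.90. Exact binomial chances of meeting the 0.8561 criterion with 78 cases are:

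| Observed-scale sensitivity | Point estimate reaches 0.8561 (67/78) | Lower bound reaches 0.8561 (71/78) |
|---|---|---|
| 0.80 | 12% | 0.7% |
| 0.85 | 49% | 8.6% |
| 0.90 | 91% | 47.5% |

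Section 9.7.1 as worded applies the criterion to the lower bound. A moderate lift, if it occurred, could change the conclusion under either reading. The documents give no value for g.

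**5. Precision cost of losing cases.** The lower bound is 0.90 − 1.645·√(0.90 × 0.10/n), using the usual binomial standard error (the printed formula shows a minus sign where a product is needed).
- n = 78: 0.844; n = 39: 0.821.
- n = 200 (assumed): 0.865; n = 100: 0.851.

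**The case against.** **Unseen material.** The study design figure, both appendices and the cited model paper cannot be read here, and a window rule or a list of excluded inputs could sit in any of them. This stands as a limit on confidence. It does not undo the index definition, which Sections 9.1 and 9.3 state in full. If a closing rule exists, a cross-reference would settle the point.

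**The objective.** Section 8 asks for performance against chart diagnosis among heart failure patients, not for performance before recognition. Early diagnosis appears as a hedged sentence in the background. This stands too: the primary result remains estimable and need not be replaced. What is affected is the use a reader may make of it.

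**An existing check.** Earliest-date indexing would often precede recognition, given the mean of 6.1 years to diagnosis in Section 7. That is fair, but the analysis is conditional, is not tied to the amyloid date, and can still fall after recognition in a patient who joined a contributing network late.

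**Stronger readings.** A reader might infer three things that the documents do not support.
- That the amyloid code feeds the model and makes the result circular. The abstract says E85.82 defined the patients of interest in development, so it is unlikely to be an input. If no amyloid or work-up code is an input, only fuller coding of related conditions remains, and the effect is smaller.
- That the plan contradicts itself. The phrase "along with their diagnosis codes listed in all their records" can be read as all pre-index records, so this is a wording point.
- That the survival-based percentages bound the bias. They show opportunity only.

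**Conclusion.** The point holds as a gap in what the study can show, not as a demonstrated bias. Latest-date indexing of patients already diagnosed allows features from during or after the amyloid work-up, and the readable plan neither prevents this nor commits to measuring it. Primary sensitivity may be higher than in patients not yet recognised. The size cannot be derived: it depends on the model inputs and on the share of cases indexed after recognition, and neither is in the readable documents. The figures in the working rest on assumed recording, network loss, s₀ and g, and are illustrations. The direction of any effect on specificity cannot be determined. The change is worth making because it is cheap and leaves the primary analysis intact. Confidence is moderate because of the unseen appendices, figure and model specification.

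**What to change.** Keep the primary analysis and the fixed algorithm as they are, and make four changes.

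1. Make the earliest-date analysis firm for all patients with 12 months of activity before that date. Report it beside the primary result, with the numbers of cases and controls lost.
2. Report the share of cases whose primary index date falls after their first structured amyloid code or amyloid-specific test, using a code list fixed before the model is run. Report also the number of cases with no such record.
3. Add one supportive analysis that uses only features recorded before that first record. Give cases and controls the same fixed look-back length, and assign controls a reference date, for example drawn from the distribution in cases. Exclude and count cases without a structured record. Without these rules, a shorter look-back in cases alone could lower sensitivity and be mistaken for removed inflation.
4. In the abstract and Section 9.7.1, refer to the pre-index period of Section 9.1. Add the issue to Section 9.9, and rest any statement on early identification on the analyses in items 1 and 3.

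The work is protocol text, a short code list and added model runs on structured data already planned for use, with no further chart abstraction. The supportive analyses will have fewer cases and wider intervals, as step 5 of the working shows. The first structured record may also come later than first clinical suspicion, so item 3 may not remove all coding linked to the work-up. These analyses should sit beside the primary result, not replace it.

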9.2.1. Inclusion Criteria

Primary Analysis

This study will include HF patients (defined as having ≥ 1 claim for HF or HF treatment) ≥ 50 years old with clinical diagnosis of ATTRwt-CM or non-amyloid HF ascertained by charts. Patients will be required to have ≥ 12 months of continuous activity in the EHR or claims prior to the Index Date.

Sensitivity analysis (pending feasibility assessment)

1. The earliest HF diagnosis or treatment date as the index date
2. Patients without HF diagnosis or treatment (pending feasibility assessment)
3. High Risk Population:

PFIZER CONFIDENTIAL

CT24-WI-GL02-RF02 4.0 Non-Interventional Study Protocol Template For Secondary Data Collection Study

01-Jun-2022

Page 15 of 25

- Age 65+
- Male gender
- Presence of carpal tunnel syndrome

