9.8. Quality Control

All codes and/or code algorithms will be reviewed by the clinical lead from Pfizer, as well as the protocol authors. The study team will be responsible for upholding high levels of quality control throughout the data analysis and reporting processes. Quality control (QC) checks will be performed on all Python programming, data tables, and reports generated in the course of this research. QC findings and documentation of remedial action will be maintained. Storage of programming, data, and reports will be carried out per standard procedures.

In the validation study, after the Optum NLP team creates key term tags for use in the snippet review for the two Optum clinicians who will review patient notes with these key terms mentioned, the two clinicians will record their findings from the notes regarding whether the notes support a ATTRwt-CM or non-amyloid HF. These results will be provided to the Pfizer study team for review and any clarifications or questions will be managed between the two groups until resolved.

PFIZER CONFIDENTIAL

CT24-WI-GL02-RF02 4.0 Non-Interventional Study Protocol Template For Secondary Data Collection Study

01-Jun-2022

Page 20 of 25

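### Controls are labelled non-amyloid HF from existing notes, with no amyloid test required in the readable text, so undiagnosed ATTRwt-CM that the model flags counts as a false positive and can bias specificity downward

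*Combined protocol and SAP*

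**What the plan says.** - **Disease.** Section 7 states that "diagnostic delay and misdiagnosis of ATTR-CM is common", "with a reported mean time to diagnosis of 6.1 years in ATTRwt-CM". It presents a screening tool as a way to raise suspicion of the disease.
- **Population and label.** Section 9.2.1 admits HF patients "with clinical diagnosis of ATTRwt-CM or non-amyloid HF ascertained by charts". Under Section 9.6, key terms are used to pull note snippets for review, and cases and controls are then classed as validated or not. Section 9.8 adds that "the two clinicians will record their findings from the notes regarding whether the notes support a ATTRwt-CM or non-amyloid HF". None of these sections requires an amyloid test for a control. Section 9.1 refers to Appendix A for the detailed method, but that is an embedded file and cannot be read here.
- **Timing.** Section 9.1 says that patients "will be identified from the Optum EHR database between 01 January 2018 and 30 April 2023", and "Patients will be indexed at their latest heart failure diagnosis or treatment date". At least 12 months of prior activity is required, and "There will be no minimal follow-up period for patients in this study".
- **Scoring.** Table 1 in Section 9.7.1 has two chart columns, ATTRwt-CM and non-amyloid HF. Any model-positive patient in the second column is a false positive.
- **Definition.** Section 9.5 defines specificity in terms of people who do not have the disease, with null value 0.72 and alternative 0.82.
- **Limitations and sensitivity analyses.** Section 9.9 covers out-of-network care, entry errors, missing data and non-random selection. It does not mention undiagnosed disease among controls. The sensitivity analyses in Section 9.2.1 change the index date or the population; none is described as changing the control label.

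**The concern.** The tool is meant to find patients whose disease clinicians have not recognised. If such a patient sits in the control group because the notes never raised amyloid, a correct flag is charged to the model as an error. Specificity is one of the two primary claims, and Section 9.5 defines it by disease status rather than by what the chart happens to record. The estimate could therefore fall below the model's true specificity for a reason that is not model error. The report would have no way to tell a real false positive from a patient the tool had rightly picked out.

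**Working it through.** **Inputs.** Section 9.5: alternative sensitivity 0.90, null and alternative specificity 0.72 and 0.82, margin 0.10, 90% power, stated sizes 78 and 128, and about 422 control charts to be reviewed. Section 9.7.1: one-sided 95% bound (z = 1.645), specificity cut point 0.7761. The share pi of chart-labelled controls with undiagnosed ATTRwt-CM is not in the documents; it is assumed and shown over a range.

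**1. The plan's own figures.** N = (z₀.₉₅ + z₀.₉₀)² · p(1 − p) / M², with M = 0.10.
- Sensitivity, p = 0.90: 77.07, rounded up to 78 (stated 78).
- Specificity, p = 0.82: 126.40, rounded up to 127 (stated 128).
- Specificity cut point: 0.82 − 0.10 × 1.2816 / (1.6449 + 1.2816) = 0.7762 (stated 0.7761).

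The plan's figures reproduce to within rounding.

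**2. Observed specificity with undiagnosed disease among controls.** A disease-free control is scored negative with probability 0.82. An undiagnosed case is scored negative only when the model misses it, with probability 1 − 0.90 = 0.10. So

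observed specificity = (1 − pi) × 0.82 + pi × 0.10 = 0.82 − 0.72·pi.

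Missed undiagnosed cases count as true negatives, and this partial offset is already in the formula. Observed specificity equals the cut point at pi = (0.82 − 0.7761)/0.72 = 6.1%, and the null value at pi = 0.10/0.72 = 13.9%.

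**3. Effect on the test.** Success means that the one-sided 95% lower bound, p̂ − 1.645·√(p̂(1 − p̂)/n), is at least 0.72. That needs at least 100 of 128 or 319 of 422 controls scored negative. Exact binomial power:

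| pi (assumed) | Observed specificity | Power, n = 128 | Power, n = 422 |
|---|---|---|---|
| 0 | 0.820 | 89% | >99% |
| 1% | 0.813 | 85% | >99% |
| 3% | 0.798 | 73% | 98.6% |
| 5% | 0.784 | 58% | 92.6% |
| 10% | 0.748 | 22% | 38% |

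If the model flags undiagnosed cases with probability 0.80 instead, the slope is 0.62. At pi = 5% observed specificity is then 0.789, and power is 63% (n = 128) or 96% (n = 422).

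**4. Dependence on the decision rule.** Section 9.7.1 can be read in other ways, and the choice matters at n = 422:
- Point estimate at or above 0.7761: 0.99, 0.87 and 0.66 at pi = 0, 3% and 5%.
- Lower bound at or above 0.7761: 0.76, 0.34 and 0.13.

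The gap between these figures and the table comes from the fixed cut point, which corresponds to a bound of 0.72 only near n = 128. It is a separate matter from the control label.

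**The case against.** **The control criteria cannot be seen.** Appendix A may require a negative amyloid work-up. If so, contamination shrinks or disappears. This stands: what can be said is that the readable text sets no such requirement, not that contamination is present.

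**Follow-up is not the cause.** A reader might infer that the missing follow-up rule creates the problem, or that an identification window of 5 years 4 months is too short against a 6.1-year mean delay. The documents support neither reading. Section 9.1 confines the model's features to the pre-index period, but no section confines the reviewed notes to it. Indexing at the latest HF date also puts the longest available history before index. The window says when patients are identified, not how long each has had symptoms or records, and the plan does not say when the 6.1 years begin. A follow-up rule alone would not remove the error.

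**The target is the clinical diagnosis.** Section 8 aims to predict the diagnosis in the chart, and an imperfect reference is usual in retrospective validation. This stands in part. However, the plan calls the chart label ground truth, and Section 9.5 defines specificity by disease status, so the departure matters on the plan's own terms.

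**The bias is conservative.** This stands. It lowers specificity whenever the model flags undiagnosed cases more often than the 18% at which it flags disease-free controls, so it cannot create a false success on specificity.

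**The planned size absorbs most of it.** This largely stands. With 422 controls and a bound tested against 0.72, power stays above 92% up to pi = 5%. The number of validated controls may be lower than 422, and at 10% the loss is large.

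**Conclusion.** The point holds as a possible downward bias in specificity that the plan neither measures nor acknowledges. Its size is 0.72 percentage points of specificity per percentage point of undiagnosed disease among controls, given sensitivity 0.90 and specificity 0.82. At about 422 validated controls with a lower bound tested against 0.72, the test is little affected below about 5%; at 10%, power falls to 38%. At 128 controls the loss comes sooner, with 73% at pi = 3%.

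The stronger conclusion, that the study is likely to fail its specificity hypothesis with a sound model, is not supported. No value of pi is given, the control criteria are in a file that cannot be read here, and material harm at the planned size needs about 5% or more. What remains at any pi above zero is an underestimate of specificity and false positives that cannot be interpreted. This is a cheap improvement, not a flaw that invalidates the design.

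**What to change.** Unless Appendix A already does this:

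1. **Section 9.6.** Add one field to the review spreadsheet for each control, completed before the model is run: (a) amyloid tested and negative; (b) no amyloid test, but another cause of HF documented; (c) neither.
2. **Section 9.7.1.** Keep the pooled specificity as primary. Prespecify specificity in each group as supportive. Do not treat (a) and (b) together as free of contamination, because the plan itself calls misdiagnosis common and (b) does not exclude ATTRwt-CM. Note that (a) is a selected group, suspected and then cleared, and does not represent HF patients in general.
3. **Section 9.7.1.** Add a tipping-point table for pi from 1% to 10% among the untested controls, (b) and (c). For each pi, give the implied specificity in disease-free patients, (observed − pi(1 − Se)) / (1 − pi). For example, an observed 0.784 with pi = 5% and Se = 0.90 gives (0.784 − 0.005)/0.95 = 0.82.
4. **Section 9.9.** Name undiagnosed ATTRwt-CM among controls as a limitation, and give its direction.

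The cost is one extra field in charts already under review and a few extra tables. The group results will have wider intervals. The field must be filled in before scoring; sorting the false positives afterwards would look post hoc.
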